
Specific Aim 1. To conduct a clinical study with aggressive treatment for lower respiratory symptoms in the WTC EHC in order to identify a group of patients with controlled lower respiratory symptoms (CLRS) and a group of patients with persistent uncontrolled lower respiratory symptoms (ULRS).

SA1.a To test whether a three month treatment with combined high dose inhaled corticosteroids (ICS) and long acting bronchodilators (LABA) results in improved lower respiratory symptoms in patients overall.

Specific Aim 2. To test the hypothesis that discrete measures of lung physiology are associated with the status of ULRS and CLRS in patients in the WTC EHC.

SA2.a To test whether bronchial hyperresponsiveness (BHR) is associated with the status of ULRS and CLRS by comparing rates of BHR in patients with ULRS and CLRS.

SA2.b To test whether measurements of airflow and lung volume (FEV₁, FVC, FEV₁/FVC, RV/TLC) and of small airway dysfunction (impulse oscillometry) are associated with ULRS and CLRS status.

Specific Aim 3. To test the hypothesis that inflammatory markers associated with airway disease are increased in patients with ULRS compared to CLRS in the WTC EHC.

SA3.a Compare levels of an exhaled marker of inflammation (Fractional exhaled nitric oxide; FeNO) in patients with ULRS and CLRS.

SA3.b Compare levels of circulating biomarkers associated with a Th2 inflammatory response (total and allergen-specific IgE, circulating eosinophils, C-reactive protein, serum periostin) in patients with ULRS and CLRS.

Specific Aim 4. To test the hypothesis that increased rates of co-morbid conditions are associated ULRS compared to CLRS in the WTC EHC.

SA4.a Compare quantitative measures of PTSD, anxiety or depression in patients with ULRS and CLRS.

SA4.b Compare rates of chronic rhinosinusitis symptoms and probable paradoxical vocal cord motion (PVCM) in patients with ULRS and CLRS.

SA4.c Compare rates of gastroesophageal reflux symptoms in patients with ULRS and CLRS.

Background

Exposure to WTC dust/fumes/gas in the “Survivor” population

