To understand the refractory nature of these LRS, we use the World Health Organization’s (WHO) approach to severe asthma in which these patients were characterized as “difficult-to-treat” asthma or “severe therapy-resistant”^{70,71}. Possible reasons for uncontrolled asthma include:

- poor adherence with recommended medication regimens,
- treatment-resistant lung physiology and inflammation,
- the presence of co-morbid conditions, or environmental factors that aggravate symptoms⁷¹⁻⁷⁴.

We will confirm adherence and re-evaluate lung function to further characterize the underlying disease physiology including novel measurements of distal airway disease and BHR, lung inflammation to characterize disease process, and targeted co-morbid conditions.

INNOVATION

This study will fill an important knowledge gap for understanding and potential treatment of persistent LRS resulting from an environmental exposure. The measurements of distal lung function and inflammatory markers will provide novel information that will inform studies of asthma-like lower respiratory symptoms in these populations. The findings can be used to help guide therapy for this population including guidance for a subsequent reduction in the use of corticosteroids. Characterization of the underlying physiology, inflammatory response and co-morbid conditions in these patients has the

potential to provide information that can be used for other populations with airway disease, including those exposed to other environmental insults.

Study Design

Characteristics of the Research Population

Number of Subjects

Screening 300 subjects to enroll 200 subjects.

Patients will be recruited from the WTC EHC population using block stratification *a priori* to obtain a representative sampling of the monitoring population (i.e. 5 patients with recent monitoring visits, 5 patients with monitoring visits > 1 year previously). The sampling will not be stratified by race/ethnicity, age, and exposure but these variables will be adjusted in statistical analyses. We anticipate that we will telephone 300 patients for our final enrollment of 200 patients for the study.

Gender of Subjects

We intend to enroll both women and men in the approximate distribution of our clinic – 48% women, 52% men.

Age of Subjects

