2x/week in the month preceding the monitoring visit. LRS will include: wheeze, shortness of breath at rest or with mild exertion, or chest tightness. These criteria for inclusion will be confirmed during V1 with a repeat questionnaire.

Sampling strategy for screening and enrollment in V1. Patients will be recruited from the WTC EHC population using block stratification *a priori* to obtain a representative sampling of the monitoring population (i.e. 5 patients with recent monitoring visits, 5 patients with monitoring visits > 1 year previously). The sampling will not be stratified by race/ethnicity, age, and exposure but these variables will be adjusted in statistical analyses. We anticipate that we will telephone 300 patients for our final enrollment of 200 patients for the study.

Inclusion/Exclusion criteria. Detailed inclusion/exclusion criteria for subject identification for potential

enrollment include:

- Onset of LRS after 9/11/01
- Presence of LRS > 2x/week in the month preceding the monitoring visit at chart review of the WTC EHC Monitoring visit **and confirmed in V1**
- Absence of abnormal CXR or other lung disease
- ACT score ≤ 19 at monitoring visit

Detailed exclusion criteria for potential enrollment include:

- Presence of abnormal CXR
- Presence of other lung disease (e.g. ILD, sarcoidosis)
- Current or ≥ 5 p-y tobacco use
- ACT score ≥ 20 at monitoring visit

A study scheme and procedure chart is shown:

Telephone screening visit (SV)

Patients with persistent LRS will be identified from the WTC EHC data base and will be contacted by telephone or in person. Study will be described and interest in study will also be determined.

Enrollment visit (V1)

Control status will be assessed with the Asthma Control Test (ACT), a symptom-based validated instrument^{76, 77}. Questionnaires to assess detailed specific respiratory symptom frequency, current environmental exposures, and severity and co-morbid conditions of PTSD/depression/anxiety will be administered. The Modified Medical Research Council (MMRC) dyspnea scale will be completed to assess degree of dyspnea. Baseline FeNO (fractionated exhaled Nitric Oxide) and pre and post bronchodilator (bd; 360 mcg albuterol) spirometry and IOS will be obtained.

Patients will be treated in the following manner based on assessment at V1:

- Patients who have uncontrolled LRS (ACT < 20) at time of this visit will be provided with study Advair for a total of 3 months.

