Classification visit (V4): After 3 months, patients will return for their Classification. At this visit, medication use will be reviewed by noting the medication actuations, and ACT and disease-specific questionnaires for asthma control (ASUI) will be completed^{78, 79}. Screening instruments for post-traumatic stress disorder (PTSD), depression and anxiety will be completed. Blood will be obtained for total and allergen specific IgE, peripheral eosinophil measurements, and measurements of serum periostin and C-reactive protein. FeNO, pre and post BD spirometry and IOS will be performed. Patients will complete a 6 minute walk test. Patients will also undergo laryngoscopy and vocal cord assessment. If patients are unable to complete the vocal cord assessment on the same day as V4, they will be asked to return for a separate visit within two weeks of the end of study (Day 76-90) and will be compensated \$100 for this additional time and effort.

Control Classification. Patients will be classified as ULRS or CLRS based on the ACT score obtained at V4.

Specific Aim 2. To test the hypothesis that discrete measures of lung physiology are associated with patients in the WTC EHC with ULRS compared to CLRS.

Preliminary data pertinent for SA2.

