Sample size estimation

Our primary outcome will be the rate of LRS and CLRS after the 3 month adherence period (SA1). We base our sample size and recruitment on our initial analysis of the WTC EHC monitoring in which 88% of patients who had ever received ICS or ICS/LABA had an ACT score of ≤ 19 . We assume however, that many of these patients were either no longer using medication at the time of the assessment, were on minimal dose, or were non-adherent. Thus we predict by V4 that we will have a 60% rate of ULRS and a total of 200 patients would yield 120 patients who will fit criteria as ULRS and 80 as CLRS. To take into account potential screen failures and dropouts, we will approach 300 patients initially to obtain the total sample size of 200. We will include drop-outs in our intention to treat analysis as these patients can be considered for baseline analysis.

For categorical endpoints, such as BHR, PTSD and PVDMM, the sample sizes of 120 in ULRS group and 80 in CLRS group will achieve 80% power to detect an odds ratio of 2.08 at significance level of 0.05, assuming that the rate of disease is 30% in the CLRS group. A logistic regression of the ULRS vs. CLRS on a continuous,

normally distributed variable (such as depression score or log-FeNo) with a sample size of 200 observations will achieve 80% power at a 0.05 significance level to detect an OR of 1.498 for 1- standard deviation (SD) difference in the continuous covariate.

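### The drop-out rule in the sample size section cannot produce the primary ULRS/CLRS rate, which exists only for patients with a V4 ACT score

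*Combined protocol and SAP*

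**What the plan says.** All references are to the combined protocol and SAP.

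- **Primary outcome** (Sample size estimation): "Our primary outcome will be the rate of LRS and CLRS after the 3 month adherence period (SA1"). The first term is evidently ULRS, since the same paragraph goes on to predict a 60% ULRS rate by V4.
- **How the classes are assigned** (Control Classification, under the V4 description): "Patients will be classified as ULRS or CLRS based on the ACT score obtained at V4". The cut-off is not restated there; the V1 section treats an ACT below 20 as uncontrolled.
- **Drop-outs** (Sample size estimation): "We will include drop-outs in our intention to treat analysis as these patients can be considered for baseline analysis".
- **Use of the classes** (Statistical analysis of the data): ULRS versus CLRS is the grouping variable for the chi-square and Wilcoxon tests and the response in the logistic models. That section says nothing about patients who have no class.
- **Other ACT scores** (procedure chart): the ACT is also scheduled at V1, V2 and V3.
- **The number 200.** Number of Subjects has "Screening 300 subjects to enroll 200 subjects", and that section, the sampling strategy and the recruitment section all have "We anticipate that we will telephone 300 patients for our final enrollment of 200 patients for the study". Sample size estimation has "To take into account potential screen failures and dropouts, we will approach 300 patients initially to obtain the total sample size of 200", splits the 200 into 120 ULRS and 80 CLRS, and bases the continuous-covariate power on a logistic model "with a sample size of 200 observations will achieve 80% power at a 0.05 significance level".

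**The concern.** A patient who leaves before V4 has no ULRS/CLRS status. Having baseline data does not change that, so the one rule the plan gives for drop-outs cannot be applied to the outcome it calls primary. What remains is a rate among completers, described as intention to treat.

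The outcome is symptom control after three months, so it is plausible (the documents do not say) that leaving is related to control. If so, the completer rate differs from the rate among everyone who started, and the plan offers no way to see by how much. A rule chosen after the data are seen could move the primary figure.

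For Aims 2 to 4 the point is narrower: the analysis section does not address patients without a V4 class.

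A linked question is how many classified patients the study expects. Both power statements use 200 of them. If 200 is the number enrolled, every loss after V1 reduces the number that those statements rest on.

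**Working it through.** **Inputs from the plan:** 200 patients, 60% ULRS (120 and 80), significance level 0.05, 80% power, odds ratio (OR) 1.498 per SD of a continuous covariate, OR 2.08 for a categorical variable with a 30% rate in CLRS. **Assumptions:** drop-out d of 5, 10 or 20% (none is stated); 60% ULRS among completers; two-sided tests unless noted (sidedness is not stated).

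**1. Reproduce the continuous power figure.** Required n = (1.960 + 0.842)² / [0.6 × 0.4 × (ln 1.498)²] = 200.2. Power at n = 200 is Φ(√(0.24 × 200) × ln 1.498 − 1.96) = 0.7995. The stated figure reproduces, and it uses all 200 as classified patients.

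**2. Bounds on the primary rate.** Lower bound (every drop-out CLRS): 0.6(1 − d). Upper bound (every drop-out ULRS): 0.6(1 − d) + d. The span equals d. For a milder case, assume that 40 to 80% of drop-outs are ULRS: 0.6(1 − d) + 0.4d to 0.6(1 − d) + 0.8d.

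**3. Sampling error for comparison.** Width of the completers' 95% CI: 2 × 1.96 × √(0.24/n), with n = 200(1 − d).

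**4. Power if 200 means enrolled.** Put n = 200(1 − d) into the power formula of step 1. Detectable OR = exp[(1.960 + 0.842)/√(0.24n)].

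| Loss | n classified | Extreme bounds | Span (points) | CI width (points) | Milder case | Power at OR 1.498 | Detectable OR |
|---|---|---|---|---|---|---|---|
| 0% | 200 | 60% | 0 | 13.6 | 60% | 80% | 1.498 |
| 5% | 190 | 57–62% | 5 | 13.9 | 59–61% | 78% | 1.51 |
| 10% | 180 | 54–64% | 10 | 14.3 | 58–62% | 76% | 1.53 |
| 20% | 160 | 48–68% | 20 | 15.2 | 56–64% | 71% | 1.57 |

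Span and CI width are equal where d = 2 × 1.96 × √(0.24/[200(1 − d)]), which gives d = 0.147 (n about 171, width 14.7 points).

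**5. Enrolment needed to classify 200.** 200/(1 − d), rounded up: 211, 223 and 250 at 5, 10 and 20% loss.

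**6. The categorical figure.** OR 2.08 on a 30% rate gives odds of (0.3/0.7) × 2.08 = 0.891, a rate of 0.891/1.891 = 47.1%. With 80 and 120 patients, the pooled-variance two-proportion test has two-sided power of 68% and one-sided power of 79%, before any drop-out. The stated 80% is close to the one-sided result only, whereas the continuous figure reproduces two-sided. If 200 means enrolled, the two-sided power becomes 66%, 64% and 58% at 5, 10 and 20% loss.

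**The case against.** The strongest reply is that the sentence means only that drop-outs will appear in baseline description, so the fault is a loose label. That is probably its plainest meaning. It still leaves the primary rate without a rule for a missing V4 ACT, and it would not be an intention-to-treat analysis of that rate. The sentence might instead point to SA1.a, which asks whether treatment "results in improved lower respiratory symptoms in patients overall"; drop-outs do have a V1 ACT. But the analysis section names no SA1.a analysis, and a before/after change needs a post-treatment score as well.

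The size is also open to challenge. It rests on assumed losses, and at 5 or 10% even the extreme bounds are narrower than the sampling error. The milder case moves the rate by at most 1, 2 or 4 points. This stands: the omission is certain, but its effect may be modest.

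Three stronger readings are tempting, and the documents do not support them.

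- *That Aims 2 to 4 are also mislabelled as intention to treat.* The term appears once, in the sample size section, tied to baseline analysis. The section that governs Aims 2 to 4 never uses it.
- *That V1 status would stand in for the V4 class.* Because study medication goes to patients with a V1 ACT below 20, this would make every treated drop-out ULRS by construction. But the classification rule names V4, and no text allows the substitution. The classification mark at V1 in the procedure chart does not create such a rule.
- *That the documents contradict each other on 200.* Three sections say enrolled. The sample size sentence can be read as 200 left after drop-out, and the sentence after it, which gives drop-outs baseline data, points to losses after V1. It can also be read as 200 enrolled from 300 approached. It is ambiguous, not contradictory.

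**Conclusion.** The point holds. The plan states a drop-out rule that cannot yield its primary outcome; followed as written, the primary ULRS rate is completers-only under a misleading label. For Aims 2 to 4, patients without a V4 class are simply not addressed.

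That finding rests on the text alone. The size depends on a drop-out rate the plan does not give. The possible shift in the primary rate outgrows sampling error only above about 15% loss, and only if drop-outs fall almost wholly in one class. The power loss applies only if 200 means enrolled: about 2 points at 5% loss, which is small, and about 9 points at 20%. This should be corrected, but it does not undermine the study.

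**What to change.** Replace the drop-out sentence with:

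> The primary ULRS rate will cover all patients who were confirmed eligible at V1 and not deferred. A missing V4 ACT will be multiply imputed from the available V1–V3 ACT scores, baseline data and whether study medication was provided, then classed at 20. The complete-case rate and bounds (all missing ULRS, all missing CLRS) will also be shown. Drop-outs will be described at baseline against completers. Comparisons under Aims 2–4 will use patients with an observed V4 class and be labelled complete-case.

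The population must be defined because V1 is the consent and enrollment visit, yet symptoms are still being confirmed there and some patients are deferred. Complete-case analysis is acceptable for Aims 2–4 if labelled, since several of the compared measurements (FeNO, IOS, vocal cord assessment) are themselves taken at V4, so a drop-out lacks both the class and the variable.

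Then state whether 200 means enrolled or classified at V4. If enrolled, give an assumed drop-out rate and restate power or detectable ORs for the expected classified number. At the same time recheck the OR 2.08 statement and state the sidedness of both calculations, because its two-sided power is about 68% before any loss.

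The cost is SAP wording, one imputation step, one baseline table and restated power. No new data or visits are needed. The stated effects may look slightly less favourable, and drop-out in Aims 2–4 is disclosed, not repaired.

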For the duration of the study, and for a period of up to 3 years after the conclusion of the study, blood sample specimens obtained during Visit 4 will be stored in the NYU-CTSI BioRepository. Only members of the study team will have access to these samples and sample information. Samples will be labeled with the patient study identification (coded number) information only, not personal health information. The investigator will ensure that patient anonymity is maintained. Patient study identification information will be stored in password-protected computers.

Sample storage for future use

Additional blood samples that are obtained by patients who have given this optional consent will be stored in the NYU-CTSI BioRepository indefinitely and marked with the study patient identification (coded number) information only. This label will not contain personal health information (PHI). Only members of the study team will have access to these samples and sample information. Future testing will aim to better understand asthma and inflammatory markers that may be associated with the disease.

Samples will only be shared with outside investigators through a signed Materials Transfer Agreement (MTA). Patient health information linked to the samples will only be shared after the outside investigators have received Institutional Review Board approval for their studies. Results of testing on the blood samples will not be shared with patients. Subjects will be allowed to withdraw their samples at any time, at which point they will be destroyed and removed from any future analysis. Storage of samples for future use is not required for participation in the study.

Data Safety Monitoring Plan

All adverse events including unanticipated effects of the study drug, lung function studies or vocal cord assessments and protocol violations will be collected. Serious adverse events such as unanticipated urgent care visits other than for asthma exacerbations that the investigator thinks might be due to study intervention will also be collected.

Adverse events and serious adverse events will be reported on case report forms completed by the research staff and reported immediately to the Principle Investigator, [name],. The monitoring entity for this study, [name], and co-investigators [name] and [name] ,will review the data and the circumstances of the event to ensure that any required changes to the protocol or procedures are made and submitted to the IRB.

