The monitoring entity ([name], [name], [name]) will meet every 6 months to ensure protocol compliance and to review any adverse events. Documentation of these meetings and safety summaries will be maintained in the regulatory binder and reported to all regulatory bodies as required.

Throughout the study, Drs. [name], [name] and [name] will monitor the participants for adverse events. Events determined by the Principle Investigator to be unanticipated problems involving risk to subjects or others will be reported by the PI to the IRB within 5 working days as per NYUSOM IRB regulations. Other adverse events that the PI determines are not unanticipated problems involving risks to subjects or others will be reported by the PI to the IRB at the time of continuing review.

Any serious adverse events will result in a delay in the continuation of the study pending review of the Serious Adverse Event

If upon review, trends are reported from this protocol that indicate a risk to subjects or others, the protocol will be modified in accordance with the research plan and patient safety regulations to minimize any adverse events that are occurring in the study. Protocol changes will not be made prior to IRB approval unless necessary to eliminate apparent immediate hazards to the research subjects.

Data Monitoring

All research staff will be trained in Good Clinical Practice, IRB regulations and HIPAA regulations and will be responsible for data entry. Data will be collected following the consent process and will be entered in the secure NYU CTSI Redcap system within 3 days of each visit by the research staff. Data will be entered into the secure CTSI Redcap program by research staff. All primary source documents will be kept in a locked cabinet in a locked room. Protocol compliance and data verification will be performed by the investigators [name], [name] and [name], every 6 months. Random audits will be performed on every 10th primary source document and every 10th database entry to ensure data accuracy and compliance with the protocol.

Risk/Benefit Assessment

Protection against Risk

The following are risks and discomforts that patients may experience during their participation in this research study. Study staff will be trained to report adverse events to the study doctor so that risks to patient health will be minimized.

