Immunosuppression: Potential worsening of infections (e.g., existing tuberculosis, fungal, bacterial, viral, or parasitic infection; ocular herpes simplex) can occur with prolonged use. We use with caution in patients with these infections and will screen you for some of these questions by questionnaire before including you in the study. More serious or even fatal course of chickenpox or measles can occur in susceptible patients.

Hypercorticism and adrenal suppression: May occur with very high dosages or at the regular dosage in susceptible individuals.

Paradoxical bronchospasm (increase in asthma symptoms): We will discontinue Advair Discus and institute alternative therapy if paradoxical bronchospasm occurs.

Patients with cardiovascular or central nervous system disorders: We will screen you with an electrocardiogram before enrolling you in this study and will use with caution because of beta-adrenergic stimulation.

Metabolic effects: We will screen for many of these conditions in our initial evaluation but will be alert to eosinophilic conditions, hypokalemia, and hyperglycemia. We will screen for these coexisting conditions and use with caution in patients with convulsive disorders, thyrotoxicosis, diabetes mellitus, and ketoacidosis.

In addition, long-acting beta2-adrenergic agonists (LABAs), such as salmeterol, one of the active ingredients in ADVAIR DISKUS, can increase the risk of asthma-related death. Currently available data are inadequate to determine whether concurrent use of inhaled corticosteroids or other long-term asthma control drugs mitigates the increased risk of asthma-related death from LABAs but recommendations are now to prescribed LABA only with an inhaled corticosteroid, which is why we use the combination treatment.

According to current recommendations for use, we only prescribe ADVAIR DISKUS for patients not adequately controlled on a long-term asthma control medication, such as an inhaled corticosteroid, or whose disease severity clearly warrants initiation of treatment with both an inhaled corticosteroid and a LABA. We are including you in this study because your asthma or lower respiratory symptoms have not been controlled.

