Methacholine Challenge. Methacholine Challenge will not be done in anyone with current asthma or breathing problems (such as asthma causing shortness of breath or chest discomfort or wheezing on the day of the test) or low lung function. We will also not do a methacholine challenge test if you already have a response to bronchodilator on your spirometry test. The methacholine challenge will only be done after a breathing test measures your lung function to be above 70%. Methacholine challenge will not be done in anyone with known allergy to methacholine. There may be other reasons you cannot take this test. The study doctor will discuss this with you. There are other medical conditions that are affected by methacholine. If you have such a condition, your study doctor must approve of you taking the test.

This test is not likely to cause serious symptoms. Some people have coughing or a tight sensation in their chest from breathing the methacholine, but it is usually mild. About 1 in 4 subjects having this test notice some cough or shortness of breath and about 1 in 10 notices some wheezing. However, reaction to methacholine can include severe bronchoconstriction (such as a severe asthma attack) and loss in breathing function. If you develop an asthma episode during any of this procedure, we will stop the procedure and provide you with albuterol to improve your breathing. This will be provided by a physician involved in the study and you will be checked until your breathing has returned to its baseline.

Blood test. Blood will be obtained by venipuncture. We will collect a blood sample that we will store and test for markers of inflammation as part of this research study. Blood will be drawn from a vein in the arm by usual venipuncture. The risks associated with a venipuncture procedure may include pain, bruising, swelling and/or infection where the needle is put in the vein. The total amount of blood to be drawn will be 30 ml (2 tablespoons).

Vocal Cord Assessment. The vocal cord assessment involves the placement of a small camera through the nose. This is typically done after numbing the nose with topical oxymetazoline (decongestant) and topical 4% lidocaine delivered via an atomizer. The risks are nasal bleeding and discomfort with the spray. Allergies are very rare, but are possible.

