If you do experience a reaction to the medication, treatment will be administered until your condition returns to normal. The placement of the camera can result in minor discomfort in the nose for about 1-2 minutes (the typical length of the exam). Rarely (<1% of the time), there may be some minor bleeding from the nose after the exam is complete. This is usually limited and can be treated easily by the physician seeing you at the time. Patients may experience lower respiratory symptoms due to the presence of the laryngoscope and during the exercise challenge.

The vocal cord assessment will take place at the NYU Voice Center, located at [name]. Patients will be accompanied by study staff member to the NYU Voice Center. If a patient is unable to walk to the NYU Voice Center from Bellevue Hospital for any reason, a taxi will be provided at no cost to the patient.

Protection Against Risks

Protection against risks from specific procedures are described above. Furthermore, personnel will be appropriately trained in the identification and reporting of adverse events to the study doctor to minimize any potential risks or discomfort. If adverse events are reported, study will be delayed until the study doctor may determine the safest course of action, which may include withdrawal of the subject under monitoring of WTC EHC physicians. If patients experience adverse mental health events, patients may be referred to WTC EHC mental health services.

Potential Benefits to the Subjects

There are potential benefits to the subjects. This research study may change the treatment that the patient would otherwise receive. Patients will be provided with a summary of results to bring to their health care

provider that will include the results of their breathing studies, methacholine challenge test, and vocal cord assessment. This may help the health care provider to guide his or her therapy.

Investigator's Qualifications & Experience

Please see attached documents.

Subject Identification, Recruitment and Consent/Assent

Method of Subject Identification and Recruitment

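### The only SAE wording sets aside urgent care for asthma exacerbations even when attributed to the study, and the deferred vocal cord visit has no scheduled AE screen

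*Combined protocol and SAP*

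**What the plan says.** The Data Safety Monitoring Plan first states that all AEs will be collected, and it names effects of the study drug, the lung function tests and the vocal cord assessment. It then adds SAEs: "Serious adverse events such as unanticipated urgent care visits other than for asthma exacerbations that the investigator thinks might be due to study intervention". This is the only description of an SAE in the document. No seriousness criteria (death, threat to life, hospital admission) appear anywhere.

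AEs and SAEs alike are entered on case report forms and "reported immediately to the Principle Investigator", after which the monitoring group reviews them. One consequence is attached to SAEs alone: "Any serious adverse events will result in a delay in the continuation of the study pending review of the Serious Adverse Event". The plan also says that if, on review, "trends are reported from this protocol that indicate a risk to subjects or others, the protocol will be modified". Under Protection Against Risks there is a further rule: "If adverse events are reported, study will be delayed until the study doctor may determine the safest course of action".

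The Risk/Benefit Assessment names these asthma-type harms of taking part:

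- Breathing may worsen when inhalers are withheld for 8 hours before testing.
- The study drug may cause paradoxical bronchospasm ("We will discontinue Advair Discus and institute alternative therapy if paradoxical bronchospasm occurs"), and its long-acting bronchodilator may raise the risk of asthma-related death.
- For the methacholine challenge, "reaction to methacholine can include severe bronchoconstriction (such as a severe asthma attack) and loss in breathing function".

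The procedure chart places AE screens at V2, V3 and V4, and the vocal cord assessment at V4. The Classification visit (V4) text lets a patient who cannot complete that assessment on the day return for it separately (Day 76-90). The chart has no column for that return visit.

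**The concern.** The exclusion covers the kind of event that the risk text warns about. Leaving background asthma attacks out of SAE counts can be defended in this population, but that reason does not reach an attack that the investigator believes the study caused. If staff follow the sentence, an attributed urgent care visit for asthma is recorded as an ordinary AE. SAE counts could then understate serious respiratory harm, and the delay pending SAE review need not start.

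The exclusion also rests on a term that the protocol does not define. The Respiratory management text says that these patients are described as having lower respiratory symptoms rather than asthma, so deciding which visits are for an asthma exacerbation is left to judgement.

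The chart raises a smaller question: whether a reaction to the vocal cord assessment would be asked about in a scheduled way, above all when the assessment is done at the separate visit.

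**Working it through.** There is no figure in the plan to reproduce. The check is of wording and of the schedule.

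**Step 1: parse the SAE sentence.** The closing clause on the investigator's opinion can attach in three ways.

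- To the urgent care visits: the example is attributed visits for reasons other than asthma, so every asthma visit is outside it, attributed or not.
- To the exacerbations: the visits set aside are those for attributed exacerbations, so unrelated asthma visits are inside the example and related ones outside.
- To SAEs in general: the example still sets aside asthma visits.

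An attributed urgent care visit for asthma is outside the example on all three.

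**Step 2: set events against consequences.**

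| Event | Collected as AE | Within the SAE example | Delay pending SAE review |
|---|---|---|---|
| Urgent care for asthma, attributed to the study | Yes | No, on any reading | Not required |
| Urgent care for asthma, not attributed | Yes | Depends on reading | Depends on reading |
| Unanticipated urgent care for another cause, attributed | Yes | Yes | Required |
| Hospital admission or death from asthma | Yes | Not addressed | Not settled by the wording |

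The first row is the defect.

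**Step 3: would deleting the exclusion be enough?** No. The example is also limited to unanticipated visits. A harm named in advance in the risk text could be judged anticipated and fall outside the example for that reason.

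**Step 4: count AE screens in the chart.**

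- Total: V2 (week 4), V3 (week 8), V4 (week 12) = 3.
- Methacholine at V3: one screen at the same visit and one later, at V4.
- Vocal cord assessment at V4: one screen at the same visit, order not stated. No contact is scheduled after V4, so the order decides whether that screen can pick up a reaction to the assessment.
- Deferred vocal cord visit: 0.

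The V2 text includes a query about adverse effects, and V3 is described as similar. The V4 text mentions none, so for V4 the chart is the only source.

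**The case against.** Much of the case on the other side stands.

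A reader might infer that asthma events go unrecorded. They do not: all AEs are collected, go at once to the principal investigator and are reviewed. Trends can change the protocol, and investigators monitor throughout the study.

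A reader might infer that admissions and deaths from asthma are excluded. The wording is an example and sets aside only urgent care visits.

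A reader might infer that a methacholine attack in general escapes the SAE rule. The Methacholine Challenge text has the procedure stopped, albuterol given by a study physician, and the patient checked until breathing is back to baseline. An urgent care visit arises only if the patient is sent on or worsens later.

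A reader might infer that no AE screen follows the V4 vocal cord assessment. That is not established, because the chart puts both at V4 and does not order them. Effects of the assessment are expressly among the AEs collected, and staff accompany patients to it.

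Two other routes soften the gap without closing it. Unanticipated problems involving risk go to the IRB within 5 working days, but that turns on the investigator's judgement, and other AEs wait for continuing review. The AE rule under Protection Against Risks also delays the study, but until the study doctor decides. Since the action may be withdrawal of the subject, it can be read as a rule about one patient, whereas the SAE rule calls for review of the event before the study continues.

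**Conclusion.** The point holds as a gap in classification and in the delay rule, not in collection. The one sentence that tells staff what an SAE looks like points them away from attributed urgent care visits for asthma, a harm of the kind that the protocol itself names. The schedule point holds in a limited form: no AE screen is scheduled at the deferred vocal cord visit, and the order at V4 is unspecified.

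The size in events cannot be given. The documents state no rate of urgent care for asthma and no expected number of deferred visits. Classification as ULRS or CLRS and the power calculation are not affected. The conclusion assumes that staff apply the sentence as written; a site that already uses standard seriousness criteria would lose less. The change is worth making because it is cheap and concerns safety.

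**What to change.** 1. In the Data Safety Monitoring Plan, delete the word unanticipated and the phrase that sets asthma exacerbations aside. Class an event as an SAE if it is fatal, life-threatening or leads to hospital admission, or if it is urgent or emergency care for asthma that the investigator thinks might be due to the study. Record attribution as a separate item.
2. Keep the delay for any SAE as it stands. Limiting it for asthma events to a set number of days after a procedure may look like a way to avoid delays for background attacks, but it would narrow the current rule. It could miss drug-related bronchospasm seen in urgent care outside the window, or an asthma death without admission.
3. State that the V4 AE screen is done after the vocal cord assessment, and add a chart column with an AE screen for the deferred visit.

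The cost is a rewritten SAE sentence, one chart note and one chart column. The downside is that a few more events will need SAE review, with the delay that goes with it. Unrelated asthma visits that meet no seriousness criterion stay ordinary AEs, which limits that burden.
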